STUDY PROTOCOL

NCT04606199

IRB ID: 19-27198

Examine the Effects of Meditation on Daily Psychological Stress Responses in Woman With a History of Child Adversity

Document date: November 4, 2021

Study design: The study uses a small micro-randomized trial design—a design that randomly assigns an intervention at each notification time point. In the proposed study, participants use the study app for 30 days and receive up to 3 notifications/day (morning, afternoon, evening). At each notification time point, participants first complete a brief ecological momentary assessment of their current psychological states (feeling stressed, positive/negative affect, stress appraisals, perseverative cognitions). Then, at each notification, each participant is randomized (50% probability) to either receive a brief mindfulness-based intervention (randomly selected from a pool of interventions) or no intervention. Thus, participants are randomized many times over the study (and each intervention is randomized many times to each person). Psychological states are again measured about 15 minutes after a notification to compare proximal (within 15 min) changes in intervention targets following an intervention vs. no intervention (proximal treatment effect).

Human Subjects Involvement, Characteristics, and Designs

I will recruit a new sample of adults, all of whom are women exposed to early life adversity. The rationale for my focus on this population is informed by the detrimental health effects of early life adversity, and by a lack of empirically-based non-pharmacological interventions to buffer or reverse risk pathways.

The study aims to develop an Ecological Momentary Mindfulness-based Intervention (EMMI) that targets maladaptive daily psychological stress responses. A micro-randomized trial will test target engagement and obtain qualitative acceptability/feasibility data during the development of the EMMI.

Inclusion criteria:

- 1) female
- 2) age 30-60
- 3) ≥2 Adverse Childhood Experiences
- 4) mild depressive symptoms (Patient Health Questionnaire ≥ 5)
- 5) having a smartphone

Exclusion criteria:

- 1) non-English speaker or unable to provide informed consent
- 2) current regular mindfulness practice (>20 min/week)

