Identification of participants with heightened distress: The proposed study aims to develop and pilot test an intervention tailored for individuals who have been exposed to early life adversity. As such, the recruitment and assessment procedures will identify individuals who will have subclinical or higher depressive symptoms. Some of these participants may be experiencing particularly significant distress and require clinical services beyond what the intervention will be able to provide. Thus, major psychiatric conditions (as determined by a diagnostic interview and the 9-item Patient Health Questionnaire, PHQ-9), including current moderately severe depressive symptoms (PHQ-9 ≥ 15) and self-harm or suicidal ideation (e.g., participant endorsed item 9 on PHQ-9: "Thoughts that you would be better off dead or of hurting yourself in some way") are an exclusion criterion. [name] study and mentoring team will immediately intervene and make appropriate referral for community care for participants. The study team will closely monitor depressive symptom severity and suicidal ideation among enrolled participants via weekly administration of the PHQ-9. Participants are instructed to make immediate contact with study personnel with any issues, questions, or concerns regarding worsening symptoms. At the first assessment visit, regardless of their current expressions of distress, participants are provided study contact information as well as local therapeutic and crisis resources. All study staff will be trained to probe for suicidal thoughts, intent, and psychotic behavior. If there is any suspicion of suicide risk or if participant endorses item 9 on the PHQ-9, study staff will immediately contact [name] so that appropriate steps can be taken to ensure the safety of the participants. [name] is a clinical psychologist who has extensive experience in assessing suicidal ideation and treating depression. She is a licensed Psychologist in the State of California. [name] and her study team will follow a written protocol for assessing and responding to suicide risk. This includes the evaluation of risk factors (e.g., plan, intent, access to lethal means) and protective factors (e.g., social support). For imminent risk, study staff will call emergency services and remain with the participant until emergency services arrive. For low to medium risk, study staff will provide mental health resources or psychological referrals, if needed.

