There is strong conceptual basis to predict the benefit of a mindfulness-based ecological momentary intervention, including for participants with early life adversity. The minimal risks participants may experience in this study are reasonable in relation to anticipated benefits. Participants may experience improved psychological responding to daily stressors, improved mental and physical symptoms, as well as improved physiological markers as a result of daily mindfulness practices that are incorporated into everyday life. In the long-term, there are substantial benefits to be gained by developing and evaluating a mindfulness-based ecological momentary intervention to improve daily psychological stress responses, and ultimately to reduce or reverse psychological risk pathways associated with early life adversity.

IMPORTANCE OF THE KNOWLEDGE TO BE GAINED

Despite evidence that early life adversity can have detrimental consequences for midlife mental and physical health, there is a paucity of mechanism-focused non-pharmacological interventions. As a result of the proposed study, we will learn more about the psychological mechanisms linking early life adversity with midlife health outcomes, which will inform intervention targets, and about the acceptability, feasibility, and adherence of a mindfulness-based ecological intervention. This research will provide the preliminary data needed to evaluate the intervention in an adequately powered study.

STATISTICAL ANALYSIS

Using the centered and weighted least square method, which has been recommended for the analysis of proximal treatment effects in micro-randomized trials, I will test proximal (within 15 min) target engagement (also termed “proximal treatment effect”) by comparing changes (from current states at notification to about 15 min later) in each primary intervention target (positive/negative affect, threat/challenge appraisal, perseverative cognition) after an intervention vs. no intervention.

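### The change-score analysis names no control variable; adding each target's notification rating would cost almost nothing and usually gain a little precision

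*Combined protocol and SAP*

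**What the plan says.** The whole analysis plan is one sentence under Statistical Analysis. The method is given as "Using the centered and weighted least square method, which has been recommended for the analysis of proximal treatment effects in micro-randomized trials". The outcome and contrast are given as "comparing changes (from current states at notification to about 15 min later) in each primary intervention target", after an intervention versus after none. The primary targets are positive and negative affect, threat and challenge appraisal, and perseverative cognition. No control variable is named there or anywhere else, and none is ruled out.

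The Study design section fixes the order of events at each prompt. First, "participants first complete a brief ecological momentary assessment of their current psychological states". After that: "Then, at each notification, each participant is randomized (50% probability) to either receive a brief mindfulness-based intervention". The second rating comes about 15 minutes after the notification. With up to three notifications a day for 30 days, a woman can be randomized up to 30 × 3 = 90 times.

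On the study's purpose, the Study design section says "The study uses a small micro-randomized trial design", Protection Against Risk says "The proposed study aims to develop and pilot test an intervention tailored for individuals who have been exposed to early life adversity", and the section on the importance of the knowledge says "This research will provide the preliminary data needed to evaluate the intervention in an adequately powered study".

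**The concern.** A change score uses the notification rating, but in a rigid way: it subtracts the whole of it, as if a woman one point higher at notification would on average still be one point higher 15 minutes later. Momentary ratings usually regress towards their average, so the true slope is likely to be below 1. Subtracting too much leaves noise in the outcome that the notification rating could have removed.

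The rating is taken before each randomization and the allocation probability is a constant 0.5, so it is independent of assignment and can go into the model safely. The estimator named in the plan accepts control variables.

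Precision is what is at stake, not validity. The study is described as small and is meant to supply preliminary estimates for a later, larger trial, so precision available from data already collected is worth taking. Naming the covariate in advance also removes the freedom to choose it target by target once results are known.

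**Working it through.** The plan gives no power, effect size, SD, correlation or sample size, so there is no figure of its own to reproduce. All inputs below except the allocation and the maximum number of prompts are assumptions, shown over a range.

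**Inputs**
- Allocation 0.5 at each prompt; at most 90 prompts per woman (Study design).
- T, answered prompts per woman: 54 (assumed 60% of 90) or 90.
- ρ, pooled pre/post correlation, including stable differences between women: 0.5, 0.7, 0.9 (assumed).
- k, SD of the 15-minute rating divided by SD of the notification rating: 0.9, 1, 1.1 (assumed). The notification SD is set to 1.
- τ, between-woman SD of the effect in notification-SD units: 0 to 0.3 (assumed).

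**Formulas**

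With half the prompts in each condition, the variance of the mean effect is proportional to τ² + 4R/T, where
- unadjusted change: R = 1 + k² − 2kρ;
- adjusted for the notification rating: R = k²(1 − ρ²).

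The difference between the two R values is (1 − kρ)². It is never negative, and it is zero only when the slope kρ equals 1. The excess standard error of the unadjusted analysis is 1/√(variance ratio, adjusted over unadjusted) − 1.

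**Worked case**

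Take ρ = 0.7, k = 1, T = 54, τ = 0.2.
- Unadjusted: R = 2 − 1.4 = 0.60; variance 0.04 + 4(0.60)/54 = 0.0844.
- Adjusted: R = 1 − 0.49 = 0.51; variance 0.04 + 4(0.51)/54 = 0.0778.
- Ratio 0.921; excess standard error 1/√0.921 − 1 = 4%.

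**Results: excess standard error of the unadjusted comparison**

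| k | T | τ | ρ = 0.5 | ρ = 0.7 | ρ = 0.9 |
|---|---|---|---|---|---|
| 1 | any | 0 | 15% | 8% | 3% |
| 1 | 54 | 0.1 | 13% | 7% | 2% |
| 1 | 54 | 0.2 | 9% | 4% | 0.7% |
| 1 | 54 | 0.3 | 6% | 3% | 0.4% |
| 1 | 90 | 0.2 | 7% | 3% | 0.5% |
| 0.9 | any | 0 | 22% | 15% | 11% |
| 0.9 | 54 | 0.2 | 12% | 7% | 3% |
| 1.1 | any | 0 | 11% | 4% | 0% |
| 1.1 | 54 | 0.2 | 7% | 2% | 0% |

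The gain shrinks as τ grows because adjustment cannot reduce τ². At k = 1, T = 54 and τ = 0.2, τ² is already 35%, 47% and 73% of the unadjusted variance at the three correlations. There is no gain when, for example, k = 1.25 and ρ = 0.8, because 1.25 × 0.8 = 1.

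**Simulation check**

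Assumed: 30 women, 54 answered prompts each, mean effect 0.10 SD, intraclass correlation 0.4, equal SDs, 4,000 replicates. Variance ratios at ρ = 0.5 / 0.7 / 0.9:

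| τ | Simulated | Formula |
|---|---|---|
| 0 | 0.740 / 0.848 / 0.954 | 0.750 / 0.850 / 0.950 |
| 0.1 | 0.764 / 0.874 / 0.979 | 0.780 / 0.878 / 0.970 |
| 0.2 | 0.823 / 0.927 / 0.984 | 0.838 / 0.921 / 0.986 |

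All nine formula values lie within the Monte Carlo 95% limits (at most about ±0.024). Mean estimates were 0.098 to 0.101 with and without adjustment, so neither analysis is biased. With only 15 women, simulated ratios of 0.72 to 0.98 still favoured adjustment in every setting.

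Once the notification rating is in the model, using change or the 15-minute rating as the outcome gives the same treatment estimate (largest difference about 1e-15). Only the coefficient of the covariate moves, by exactly 1.

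**The case against.** Nothing stated in the plan is wrong. The sentence is silent on an optional covariate, and the authors may intend to include it. That is true, and it is why this is a suggestion and not an error. As written, though, a reader cannot tell which analysis will be run.

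The largest gains also need a low correlation. With an intraclass correlation of 0.4, a pooled ρ of 0.5 implies a within-woman correlation of only (0.5 − 0.4)/0.6 = 0.17 between ratings about 15 minutes apart, which looks low; 0.7 and 0.9 imply 0.50 and 0.83. On those two columns, with equal SDs, 54 prompts and τ of 0.1 to 0.3, the excess is between 0.4% and 7%. This stands, and is why the gain is called modest.

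The covariate is not strictly free in a small sample. If inference used a t reference losing one degree of freedom per coefficient (an assumption; going from 13 to 12 with 15 women and from 28 to 27 with 30), the critical value would rise by 0.85% or 0.17%. That can offset the gain where it is already below 1%, but not elsewhere.

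The statement about bias needs a condition. Protection Against Risk lets women skip assessments. If missing 15-minute ratings depended jointly on assignment and the notification rating, the unadjusted comparison could be biased. In one illustrative simulation of this kind (true effect −0.20), the bias was +0.058 unadjusted and +0.018 with the rating included. This is a separate, hypothetical issue, and it too favours including the rating.

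Centering the rating on each woman's own mean did somewhat better in simulation (variance ratios 0.75 to 0.95, against 0.82 to 0.97 for the raw rating). A whole-study mean, however, includes ratings recorded after the randomization being analysed, so the raw rating is the safer choice.

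**Conclusion.** The point holds, as a minor one. Omitting the notification rating does not itself bias the comparison, provided missing 15-minute ratings do not depend jointly on assignment and that rating. It generally costs some precision. Over the assumed ranges the unadjusted standard error is between 0% and 22% larger. With equal SDs, moderate variation in effect between women (τ = 0.2) and 54 answered prompts, it is 9%, 4% or 0.7% larger at correlations of 0.5, 0.7 or 0.9. Every one of these figures rests on assumed correlations, SD ratios, response rates and effect variation, because the documents give none. No power claim in the plan depends on the choice, and in a pilot it would rarely change a conclusion.

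**What to change.** Add one sentence to the statistical analysis section, for example:

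> For each primary target, the centered and weighted least squares model of the change will include that target's rating at notification as a control variable, with the treatment indicator centered at 0.5.

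The outcome can stay as change. Report the unadjusted change comparison as a sensitivity analysis.

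The cost is that sentence and one further estimate per target. No new data are needed, and the outcome, the estimator and the conduct of the trial are unchanged.

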Psychological distress from audio-recorded qualitative interview: Audio-recorded semi-structured interviews will obtain qualitative information on the acceptability and feasibility of the Ecological Momentary Mindfulness-based Intervention (e.g., satisfaction with each intervention component, preferred frequency/duration of assessment and intervention sessions, any challenges that participant encountered in using the app, and general feedback on app usability). Interviews carry a minimal risk for emotional discomfort and stress. Efforts will be taken to maintain the participant's comfort and study procedures will be stopped at the request of the participant.

Psychological distress from participation in the intervention: Participation in the Ecological Momentary Mindfulness-based Intervention (EMMI) includes short ecological momentary assessments (1-2 minutes/notification) and brief audio-guided mindfulness-based interventions. Previous studies of mindfulness interventions, including those recruiting individuals with early life adversity and trauma, demonstrated reduced distress (depression and anxiety), enhanced coping and mood, and improved quality of life. Thus, the EMMI carries minimal risk for emotional discomfort or stress.

Confidentiality: Participation in research may involve a loss of privacy, however information will be handled with the upmost confidentiality. One limit to confidentiality is if a participant is at imminent risk of harming herself (see more under Protection Against Risk).

Inconvenience: There may be some burden associated with filling out self-report questionnaires and completing repeated ecological momentary assessments and interventions in the flow of everyday life. However, participants will be provided with compensation for their time and effort.

ADEQUACY OF PROTECTION AGAINST RISKS

Recruitment and Informed Consent

Prior to study commencement, all procedures will be approved by the UCSF Committee on Human Research (CHR, the equivalent to IRB). Potential participants will be recruited using methods my mentors, advisors, and I have found successful in previous research with participants with high exposure to early life adversity.

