point. Lastly, a trained research assistant will also make weekly phone contact with participants to address potential difficulties with adherence.

Protection Against Risk

Participants will be told that their participation is voluntary, and they can choose to withdraw from the study at any time without further obligation.

Psychological distress from self-report questionnaires, diagnostic interviews, and ecological momentary assessments: Participants will be told that they do not have to complete any questions, interviews, assessments, or interventions they do not want to complete and can stop at any time. Participants can also contact study staff to discuss any concerns.

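### The comparison of changes uses only prompts with a follow-up rating, and the plan neither adjusts for the pre-rating nor says how missed follow-ups are handled

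*Combined protocol and SAP*

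**What the plan says.** The Study design section fixes the order of events. At each notification "participants first complete a brief ecological momentary assessment of their current psychological states". Then "each participant is randomized (50% probability) to either receive a brief mindfulness-based intervention" or none. Finally, "Psychological states are again measured about 15 minutes after a notification". The pre-rating covers the same targets as the follow-up and precedes randomization.

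The Statistical Analysis section is a single sentence. It names centered and weighted least squares and describes "comparing changes (from current states at notification to about 15 min later) in each primary intervention target", by condition. It states no control variable, no completion weight, no rule for a prompt with a pre-rating but no follow-up, and no sensitivity analysis.

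Missed follow-ups are foreseeable. Under Protection Against Risk, women are told that "they do not have to complete any questions, interviews, assessments, or interventions they do not want to complete". The Inconvenience paragraph under Potential Risks acknowledges burden from "completing repeated ecological momentary assessments and interventions in the flow of everyday life".

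**The concern.** Comparing changes by assigned condition is sound for all randomized prompts. Randomization does not balance the subset of prompts that still have a follow-up rating.

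Subtracting the pre-rating does not break its link with the change, because a high pre-rating tends to be followed by a fall. If answered prompts start from different levels in the two conditions, the difference appears as an effect of meditation or masks one. The interval in which follow-ups can be lost is also where the conditions differ: one delivers "brief audio-guided mindfulness-based interventions" and the other delivers nothing. That is a reason to expect unequal completion rates, though not evidence of them.

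This is the only analysis of target engagement that the plan states, and its result is meant to be used: "This research will provide the preliminary data needed to evaluate the intervention in an adequately powered study".

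**Working it through.** **From the documents:** 30 days x up to 3 notifications = up to 90 prompts per woman; allocation 50%; the outcome is follow-up minus pre-rating. The plan gives no sample size, completion rate, SD or effect size, so it has no figure of its own to reproduce.

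**Assumed:** 20, 30 or 50 women; 63 answered prompts each (70% of 90); pre-rating variance 1, half between women and half between prompts; within-woman pre-post correlation rho = 0.6; no average effect; between-woman SD of the effect 0.2. Where completion depends on the pre-rating, the odds ratio is 0.6 per SD.

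**Step 1: what the named method computes.** Its weights concern the randomization probability. At a constant 50% they are equal for every prompt. Without a control variable, the coefficient on (assignment - 0.5) is the difference in mean change among answered prompts.

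**Step 2: bias formula.** Let m be the share of follow-ups missed and g the mean change in answered minus missed prompts. The answered mean equals the full mean plus m x g, so bias = m1 x g1 - m0 x g0 (1 = intervention, 0 = none).

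**Step 3: size of g.** The variance of the change is 0.5 x [(1 - 0.6)^2 + (1 - 0.6^2)] = 0.4, so its SD is 0.632. The covariance of change with pre-rating is -(1 - 0.6) x 0.5 = -0.2, which gives a slope of -0.2/0.632 = -0.316 SD of change per SD of pre-rating. With odds ratio 0.6, the mean pre-rating of answered prompts is lower by about |ln 0.6| x m = 0.511 x m. Hence m x g is about 0.316 x 0.511 x m, and g is about 0.16.

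**Step 4: results** (absolute bias in SD of change; simulated values from 2,000 runs per case, except the varying-effect row, which comes from separate checks).

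| Assumed situation (completion, intervention vs none) | Formula | Simulated |
|---|---|---|
| Same link, same rates, constant effect | 0 | about 0 |
| Same link, 85% vs 75% | (0.25 - 0.15) x 0.16 = 0.016 | 0.016 (0.013 to 0.014 in separate checks) |
| Same link, 80% vs 80%, effect changes 0.2 SD per SD of pre-rating | 0.2 x 0.511 x 0.20 = 0.020 | about 0.02 |
| Link after no intervention only, 80% vs 80% | 0.20 x 0.16 = 0.032 | 0.031 to 0.032 |
| The same, 85% vs 75% | 0.25 x 0.16 = 0.040 | 0.037 to 0.040 |
| The same, 90% vs 70% | 0.30 x 0.155 = 0.047 | 0.045 to 0.047 |

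In the last three rows false positives at a nominal 5% are 5.6%, 6.4% and 8.9% with 20 women, and 8.8%, 11.6% and 16.1% with 50. With the link in one condition only, 85% vs 75% completion and 30 women, the bias runs from 0.017 to 0.065 for odds ratios 0.8 to 0.4, and from 0.050 to 0.025 for rho 0.4 to 0.8.

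**Step 5: what a correction achieves.** In the last three rows, the pre-rating as a control variable alone brings the bias to 0.004 SD or less, with slightly better precision. If the effect varies with the pre-rating, 0.014 to 0.020 SD remains; adding completion weights reduces this to about 0.001. With both, in the constant-effect cases with 20 women, the SD of the estimate was 0.074 to 0.077, against 0.077 to 0.079 for the plain comparison.

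**Step 6: what it cannot achieve.** Suppose completion depends on the unseen change, with a gap of 0.3 SD in both conditions. The formula gives (0.25 - 0.15) x 0.3 = 0.03 at 85% vs 75%, and (0.30 - 0.10) x 0.3 = 0.06 at 90% vs 70%. Simulated bias is 0.027 and 0.057; with control variable and weights it falls only to 0.024 and 0.051.

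**The case against.** The case against has real force.

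- **No unequal loss is shown.** The freedom to skip is a voluntariness safeguard. The plan also provides an app demonstration, postponement of notifications and weekly calls. These may reduce loss, but they do not say how remaining loss is analysed.
- **The largest figures need a special pattern.** The contrast of audio with nothing is a reason for completion rates to differ. No passage suggests that completion depends on the pre-rating in one condition only. With the same link in both conditions and 85% vs 75% completion, the bias is about 0.015 SD, well under one standard error in a small trial. The 16% false-positive rate also needs 50 women and 90% vs 70% completion, while 5.6% with 20 women is close to nominal.
- **Silence is not a decision against adjustment.** The named method admits control variables. A reader might infer that the plan has chosen an unadjusted analysis of answered prompts; the text only leaves the choice open. What stands is that an open choice could be settled after the data are seen.
- **Weights are not always needed.** The control variable suffices when the effect does not vary with the pre-rating.

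A reader might also infer that the pre-rating repairs every missed follow-up. Step 6 shows that it does not.

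**Conclusion.** The point holds in limited form. As written, the analysis amounts to a difference in mean change among answered prompts, a set determined after randomization. It is right when completion is unrelated to the change within each condition. It is also right when completion depends only on the pre-rating, with the same link and rate in both conditions, and the effect does not vary with the pre-rating.

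Otherwise the bias under the assumed inputs is about 0.015 to 0.05 SD of change. False positives are about 6 to 9% with 20 women and up to about 16% with 50 in the one-condition pattern. Other inputs would give other figures. The documents do not support a claim that the trial's result will be biased, or in which direction. The case for changing the plan is that the pre-rating is already collected and adjusting for it costs almost nothing.

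**What to change.** Add to the Statistical Analysis section:

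1. In the centered and weighted least squares model for each target, include the pre-rating of that target as a control variable.
2. Report follow-up completion by assigned condition.
3. As a secondary analysis for each target, weight each answered prompt by the inverse of its estimated completion probability, from a logistic model with assignment, pre-rating and their product. This also covers an effect that varies with the pre-rating.
4. For dependence on the unseen change, add a shift analysis: move the missed changes in one condition by, for example, 0.25, 0.5 and 0.75 SD, and report the shift at which the conclusion changes. The effect moves by the share missed times the shift; with 20% missed and a shift of 0.5 SD this is 0.20 x 0.5 = 0.10 SD.

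The cost is one extra covariate, one completion model and one sensitivity analysis for every target, so the work grows with the number of targets. It needs no new data and no change to the app. Step 4 does not remove bias; it shows how large the unseen difference would have to be.

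### Does it matter that the plan does not say whether the affect pair and the appraisal pair are each analysed as one score or two?

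*Combined protocol and SAP*

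**What the plan says.** The Statistical Analysis section is a single sentence. It names the estimator ("Using the centered and weighted least square method, which has been recommended for the analysis of proximal treatment effects in micro-randomized trials") and the outcome metric ("comparing changes (from current states at notification to about 15 min later"). The comparison is made "in each primary intervention target (positive/negative affect, threat/challenge appraisal, perseverative cognition".

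The Study design paragraph describes the momentary assessment as covering "feeling stressed, positive/negative affect, stress appraisals, perseverative cognitions", and says the repeat measurement serves to "compare proximal (within 15 min) changes in intervention targets following an intervention vs. no intervention (proximal treatment effect". At every notification "each participant is randomized (50% probability) to either receive a brief mindfulness-based intervention" or none.

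The document gives no instrument, item list, scoring rule or composite formula for any of these states. It also gives no sample size, alpha, power or correlation. Its stated purpose is modest: "This research will provide the preliminary data needed to evaluate the intervention in an adequately powered study".

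**The concern.** The outcome variable is the core of a primary analysis, and here two of the three listed items are slash pairs. If both pairs are combined there are three primary tests, if one pair is combined there are four, and if neither is combined there are five. The Study design paragraph does not settle this. It uses the same slash for affect and refers only generally to appraisals.

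Two analysts who both follow the sentence could therefore fit different outcomes and report different primary results. A combined score estimates a different effect from either of its members and cannot show which one moved. If only one member of a pair responds, combining dilutes the signal. If the two respond in opposite senses once coded so that higher is better, the effects cancel. A reader could also not tell from the plan whether the scoring was chosen before or after the data were seen.

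**Working it through.** **What the text supports.** The analysis is stated for each target. Nowhere does the document mention a composite, index, sum, difference or ratio. Positive affect, negative affect, threat and challenge are each nameable quantities, so reading the slash as shorthand for separate scores needs no added rule. A composite would need a formula and a common direction, and the document supplies neither. If the app happens to record a pair on a single bipolar item, there is only one score and no choice to make.

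**What separate scores cost.** Each two-sided test keeps its own error rate and its own power, and needs no declared beneficial direction. The number of tests would matter for a claim that at least one target moved. With independent tests at an assumed 0.05, the familywise rate is 1 − 0.95³ = 14.3% for three, 1 − 0.95⁴ = 18.5% for four and 1 − 0.95⁵ = 22.6% for five. The plan makes no such joint claim. It asks one question per target.

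**What a composite would do.** The document has no power figure to reproduce, so all inputs here are assumptions:

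- two-sided alpha 0.05, critical value 1.960;
- 80% power for a member that responds, so its z statistic has mean 1.960 + 0.842 = 2.802;
- equal standard errors, an equal-weight sum, and both members coded so that higher is better;
- correlation r between the two effect estimates from 0 to 0.9.

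The estimator is linear in the outcome when every score uses the same covariates and weights, so the composite estimate is the sum of the member estimates:

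z_comb = (z₁ + z₂) / √(2(1 + r)).

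- One member responds: mean of z_comb = 2.802 / √(2(1 + r)).
- Both respond equally: mean of z_comb = 2.802 × √(2 / (1 + r)).
- Equal and opposite responses: the mean is 0, so the test rejects 5% of the time.

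Power is Φ(mean − 1.960), plus a negligible opposite tail.

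| r | Mean, one responds | Power | Mean, both respond | Power |
|---|---|---|---|---|
| 0 | 1.981 | 50.8% | 3.962 | 97.7% |
| 0.5 | 1.617 | 36.6% | 3.235 | 89.9% |
| 0.9 | 1.437 | 30.1% | 2.874 | 82.0% |

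Starting from 50% power per member, the composite has 28% down to 17% if one responds and 79% down to 52% if both do.

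**Break-even.** Let the weaker member's effect be k times the stronger one's. The composite matches the stronger member's power when (1 + k) / √(2(1 + r)) = 1, so k = √(2(1 + r)) − 1. This is 0.41 at r = 0, 0.73 at r = 0.5 and 0.95 at r = 0.9. Above that value combining gains power, and below it combining loses power.

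**Sensitivity.** In the one-member case the loss shrinks if r is negative (65.8% at r = −0.3). With one-sided 0.05 the range is 54.5% down to 35.6%. A ratio score was not computed. If each score were adjusted for its own baseline, the additivity would be only approximate.

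**The case for a change.** The strongest case for acting does not depend on the power figures. The plan calls these targets primary and says it will test them, yet it leaves the outcome open. An affect balance or a threat-minus-challenge score is a conceivable reading of the slash. If separate scores are meant, one sentence would say so. The dilution is also not trivial where it occurs: in the one-member case starting from 80% power, the responding member would be significant and the composite not in 31% to 50% of studies, by simulation.

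Part of this stands. The text is silent, and a numbered list of scores would be tidier. What does not stand is that harm follows from the plan as written. The loss arises only if an analyst introduces a composite that the document never mentions, and only if one member responds alone. Nothing in the document predicts that pattern, and when both members respond the same composite gains power.

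Nor does the remark "which will inform intervention targets" raise the stakes. In its sentence, under Importance of the Knowledge to be Gained, it concerns psychological mechanisms between early adversity and midlife health, not which half of a pair shifts within 15 minutes. That feeling stressed is assessed but not listed as primary is no conflict either, since a state can be measured without being a primary target.

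**Conclusion.** No change is called for. This is missing detail that a competent analyst fills sensibly: analyse positive affect, negative affect, threat, challenge and perseverative cognition separately and report each one. That follows the sentence as written and gives sound per-target results. Choosing composites instead would be a fair trade-off, with gains when the members move together and losses when they do not. The 30% to 51% and 82% to 98% ranges describe that trade-off only under the assumptions listed above, none of which comes from the document. They are not a property of this trial. Because the study is described as small and preliminary, and no go or no-go decision is tied to any target, either reading would have limited consequences.
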